11.6.2 Secondary Analyses

11.6.2.1 Pharmacokinetics

The secondary PK parameters ($AUC_{(0-12)}$, $AUC_{(0-t^*)}$, $AUC_{(0-\infty)}$, $\%AUC_{extrap}$, t_{last} , t_{max} , λ_z and $t_{1/2}$) will be listed and summarized as described in Section 11.1 “General Considerations” and subsections. In addition plots of the data versus product will be provided.

The nicotine plasma concentrations will be summarized in a similar manner to the PK parameters but will also be split out by sample time point. Geometric mean (95% CI) profiles, spaghetti plots of all subjects and individual PK profiles for each subject will also be presented.

PK parameter and plasma concentration data will also be listed along with the details of the actual times after T_0 .

Only subjects in the PK population who provide evaluable data for both the CHTP 1.1 M and mCC products will be included in the following analyses.

- The secondary analysis of $AUC_{(0-12)}$, $AUC_{(0-\infty)}$, $AUC_{(0-t)}$ and $t_{1/2}$ will be performed on the natural log-transformed parameters using the same ANOVA model as used for the primary analysis. (Section 11.6.1 “Primary Analyses”).
- The analysis of t_{max} will be performed by calculating the difference for each subject (CHTP 1.1 M - mCC) and obtaining the Hodges-Lehmann (**Hodges and Lehmann, 1963**) 95% CI estimates. The median t_{max} for each product and the median difference between the products along with the 95% CI will be presented in the tables.

Supportive analysis will be performed as described in Section 11.6.3 "Supportive/Sensitivity Analysis" in order to evaluate the sensitivity of CHTP 1.1 M effect estimates to methods used for missing data by means of a mixed model approach, should there be 20% or more missing parameter PK model.

TFL number	Title
TABLES	
15.2.4.1	Analysis of Secondary Pharmacokinetic Parameters of Nicotine – PK Population
15.2.4.4	Descriptive Statistics of Pharmacokinetic Parameters of Nicotine – PK Population
15.2.4.4.1	Descriptive Statistics of Pharmacokinetic Parameters of Nicotine by Sex – PK Population
15.2.4.4.2	Descriptive Statistics of Pharmacokinetic Parameters of Nicotine by Nicotine Level – PK Population
15.2.4.5	Descriptive Statistics of Plasma Nicotine Concentrations (ng/mL) – PK Population
15.2.4.5.1	Descriptive Statistics of Plasma Nicotine Concentrations (ng/mL) by Sex – PK Population
15.2.4.5.2	Descriptive Statistics of Plasma Nicotine Concentrations (ng/mL) by Nicotine Level – PK Population
FIGURES	
15.1.2.1	Nicotine Plasma Concentration (ng/mL) Profiles Geometric Mean and 95% CI – PK Population
15.1.2.2	Nicotine Plasma Concentration (ng/mL) Profiles for All Subjects by Product – PK Population
15.1.2.3	Nicotine Plasma Concentration (ng/mL) Profiles by Subject – PK Population
15.1.2.4	Secondary Pharmacokinetic Parameters of Nicotine vs. product – PK Population
LISTINGS	
15.3.3.1	Listing of Pharmacokinetic Parameters of Nicotine
15.3.3.2	Listing of Additional Pharmacokinetic Parameter Data

11.6.2.2 Biomarkers

11.6.2.2.1 Exhaled CO and COHb

COHb measured in blood and exhaled CO will be investigated as a measure of exposure to CO.

CO in exhaled breath will be measured using the Smokerlyzer[®] device such as Micro+[™] Smokerlyzer[®] device or similar. A CO breath test will be conducted once at Day -3 and Day 4. On Day -2, Day -1, Day 1, Day 2, and Day 3, four CO breath tests will be done per day. On Day 1 and Day 3, the first test per day will be performed within 15 minutes prior to T₀ and then between 12:00 PM and 01:30 PM, between 4:00 PM and 05:30 PM, and between 8:00 PM and 09:30 PM. On the wash-out days (Day -2, -1 and Day 2) it will be conducted between 8:00 AM and 09:30 AM, 12:00 PM and 01:30 PM, between 4:00 PM and 05:30 PM, and between 8:00 PM and 09:30 PM.

Tests for COHb measurement will be performed at a local laboratory. Blood samples will be taken as follows at Day 1 and Day 3: a total of five blood samples will be taken. The first sample will be taken within 15 minutes prior to using the first product (T₀). Thereafter the sampling times in relation to T₀ are at 15 minutes, 60 minutes, 4 hours, and 12 hours post-T₀.

Descriptive statistics summarized by product will be produced separately for all scheduled timepoints for exhaled CO and COHb assessments at single use day. This will be done on the PK populations, overall and by the two stratification factors (sex, mCC nicotine level at Admission) as specified in Section 11.1.1 “Stratified Presentation”.

Actual values of blood COHb and levels of exhaled CO will be listed and summarized. The number of subjects with COHb levels $\leq 2\%$ will be summarized for each measurement. The 2% threshold is important because, as reported in (WHO, 2010), COHb elevated above 2% was found to cause ST-segment changes and decreased time to angina.

In addition line graphs will be produced for exposure means (and 95% CI) over all timepoints.

Values of exhaled CO measured during wash-out, admission, and discharge will not be analyzed because they will be collected only for monitoring purposes, however they will be reported as described in Section 11.4 “Measurements of Product Compliance”.

The analysis of the exhaled CO during single use days and log transformed blood COHb levels will be performed using a mixed effects ANOVA with a restricted maximum likelihood (REML) method to estimate mean differences and variances for CHTP 1.1 M vs mCC, using unstructured covariance structure (Bethesda, 2013; Brown and Prescott,

1999). Subjects nested within sequence will be used as a random effects and sequence, period, product and product*time point will be used as fixed effect factors. The model will be evaluated including all of the different assessment timepoints, excluding the assessment prior to T₀. In addition, time point will be treated as a repeated measurement.

The SAS code to be used is shown below:

```
Proc mixed data=_data_ method=reml maxiter=200;  
Class subject sequence product period time_point;  
Model log_COHb (or CO) = sequence period product time_point  
product*time_point;  
Random subject(sequence);  
Repeated time_point / subject=subject*product type=un;  
Lsmean product / pdiff =control('mCC') alpha=0.05 cl;  
Lsmean product*time_point / pdiff alpha=0.05 cl;  
Run;
```

In case of model convergence issues, this will be reported in the study report and additional covariance structures will be investigated with the following order: heterogeneous compound symmetry (type=csh), heterogeneous autoregressive (type=arh) and variance component (type=vc).

For the analysis of CO breath test, the main comparison will be the difference over all time points. LS means for each product, the overall difference and the differences at each time point will be presented in the tables as a point and interval (95% CI) estimate. Figures of the LS mean difference and 95% CI at each time point will be produced.

For the COHb analysis, the main comparison will be the ratio over all time points. LS means for each product will be back-transformed by exponentiation and presented in tables together with the point and interval (95% CI) estimate of the overall ratio and of the ratios at the different time points. Figures of the LS mean ratio and 95% CI at each time point will be produced.

The data will be presented in the below outputs:

TFL number	Title
TABLES	
15.2.4.6	Analysis of Blood COHb (%) – PK Population
15.2.4.7.1	Descriptive Statistics of Blood COHb (%) Continuous Measurements – PK Population
15.2.4.7.1.1	Descriptive Statistics of Blood COHb (%) by Sex – PK Population
15.2.4.7.1.2	Descriptive Statistics of Blood COHb (%) by Nicotine Level – PK Population
15.2.4.7.2	Descriptive Statistics of Blood COHb (%) Categorical Measurements – PK Population
15.2.4.8	Analysis of Exhaled CO (ppm) During Single Use Days – PK Population

TFL number	Title
15.2.4.9.1	Descriptive Statistics of Exhaled CO (ppm) During Single Use Days Continuous Measurements – PK Population
15.2.4.9.1.1	Descriptive Statistics of Exhaled CO (ppm) During Single Use Days by Sex – PK Population
15.2.4.9.1.2	Descriptive Statistics of Exhaled CO (ppm) During Single Use Days by Nicotine Level – PK Population
15.2.4.9.2	Descriptive Statistics of Exhaled CO (ppm) During Single Use Days Categorical Measurements– PK Population
15.2.4.10.1	Descriptive Statistics of Exhaled CO (ppm) During Days -3,-2, -1, 2 and 4 Continuous Measurements – PK Population
15.2.4.10.1.1	Descriptive Statistics of Exhaled CO (ppm) During Days -3,-2, -1, 2 and 4 by Sex – PK Population
15.2.4.10.1.2	Descriptive Statistics of Exhaled CO (ppm) During Days -3,-2, -1, 2 and 4 by Nicotine Level – PK Population
15.2.4.10.2	Descriptive Statistics of Exhaled CO (ppm) During Days -3,-2, -1, 2 and 4 Categorical Measurements– PK Population
FIGURES	
15.1.2.5.1	Blood COHb (%) Profiles Geometric Mean and 95% CI –PK Population
15.1.2.6.1	Blood COHb (%) Profiles Geometric Least Squares Mean Ratio and 95% CI –PK Population
15.1.2.7.1	Exhaled CO (ppm) Profiles During Single Use Days Arithmetic Mean and 95% CI –PK Population
15.1.2.8.1	Exhaled CO (ppm) Profiles During Single Use Days Arithmetic Least Squares Mean Differences and 95% CI –PK Population
LISTINGS	
15.3.3.3	Listing of Blood COHb Levels (%) and Sampling Times
15.3.3.4	Listing of Exhaled Breath CO (ppm) and Measurement Times

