5.2 Secondary Objectives and Endpoints

1. To evaluate the difference on nicotine pharmacokinetic (PK) absorption parameters (AUC from start of product use extrapolated to infinity [$AUC_{(0-\infty)}$], up to 12 hours [$AUC_{(0-12)}$], and partial $AUC_{(0-t')}$, where t' is the subject-specific time of maximum nicotine concentration following single use of the mCC [$AUC_{(0-t')}$]) between the CHTP 1.1 M and mCC.

Endpoints:

- $AUC_{(0-\infty)}$
- $AUC_{(0-12)}$
- Partial $AUC_{(0-t')}$

2. To evaluate the time to the maximum concentration (t_{\max}) of nicotine for the CHTP 1.1 M as compared to mCC.

Endpoint:

- t_{\max}

3. To describe the terminal half-life ($t_{1/2}$) of plasma nicotine for the CHTP 1.1 M and mCC.

Endpoint:

- $t_{1/2}$

4. To describe the differences on urge-to-smoke over time between the CHTP 1.1 M and mCC.

Endpoint:

- Urge-to-smoke questionnaire (questionnaire of smoking urges brief [QSU-brief]) total score, factor 1 and factor 2

5. To describe product evaluation of the CHTP 1.1 M and mCC.

Endpoint:

- Product evaluation questionnaire (modified cigarette evaluation questionnaire [MCEQ]) subscales scores
6. To describe the levels of carbon monoxide (CO) exposure for the CHTP 1.1 M as compared to mCC.
Endpoint:
- CO exposure biomarkers: levels of exhaled CO and carboxyhemoglobin (COHb) in blood
7. To monitor the safety during the study.
Endpoints:
- Incidence of adverse events (AEs)/serious adverse events (SAEs)
 - Respiratory symptoms: cough assessment by visual analogue and Likert scales and one open question
 - Vital signs
 - Spirometry
 - Electrocardiogram (ECG)
 - Clinical chemistry, hematology, and urine analysis safety panel
 - Physical examination
 - Concomitant medication.
 - Incidence of CHTP 1.1 M malfunctions and misuse. [REDACTED]

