**Figure 1 Study Flow Chart****2) The Investigational Period (from Day -2 to Discharge):**

The Investigational period will consist of 2 periods (Period 1, Period 2) with each period consisting of approximately 48 to 57 hours smoking abstinence and 1 day of single product use.

Period 1: From Day -2 to Day 1. After Day 1 product use, the subject will start his/her washout for period 2

Period 2: From Day 2 to Day 3. The products should be used at the same time (within 1 hour) on Day 1 and Day 3

48 eligible, healthy smoking subjects will be randomized to one of 2 sequences:

Table 1 Definition of Randomization Sequences

Sequence	Sample Size
1. CHTP 1.1 M then mCC	24
2. mCC then CHTP 1.1 M	24

Each sex and smoking strata (International Organization for Standardization [ISO] nicotine levels ≤ 0.6 mg vs. >0.6 to 1.0 mg) will have a quota applied to ensure they represent at least 40% of the study population for each Sequence (Sequence 1 and Sequence 2).

Subjects who do not complete the study after randomization will not be replaced.

Subjects will be discharged from the investigational site in the morning of Day 4 after performance of Discharge assessments.

3) The Safety Follow-up Period (from Discharge until Day 11):

A 7-day safety follow-up will be done for the recording of spontaneously reported AEs and SAEs (passive surveillance) and the active follow-up by the investigational site of AEs/SAEs ongoing at Discharge. Any AE will in general be followed-up until resolved, stabilized (*i.e.*, no worsening of the event), or until a plausible explanation for the event has been found.

The end of study for the subject is defined as the date of completion or discontinuation on Subject status form completed. AEs/SAEs not resolved or not stabilized at EOS are to be recorded as ongoing at EOS.

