9 CHANGES FROM THE PROTOCOL SPECIFIED STATISTICAL ANALYSIS

The analyses of Adverse Events will be performed by sequence; and by sequence and period if there are more than 10 AEs. The other safety evaluations will also analyzed by sequence and study day.

Shift tables for safety endpoints will not be produced for this study, because the relevant information will be provided in listings.

Statistical analysis for blood COHb (%) and exhaled CO (ppm) measurements and the QSU-brief questionnaire data will be performed including interaction terms for product and time point to enable LS means to be calculated at each time point in order to explore the pattern of the CHTP 1.1 M effect over time. The main comparison between products will be the comparison over all time points.

Serology for human immunodeficiency virus (HIV) 1/2 cannot be transferred because of privacy laws, therefore this endpoint is not presented in listings.

In addition to the PK parameters mentioned in the protocol, %AUC_{extrap} will be listed, as this parameter contains important information on the quality of the AUC_(0-∞).

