11.1.4 Definitions for Statistical Data Analysis

The following definitions (Table 14) for statistical analyses/presentations will be used:

Table 14: Timepoint Definitions

Term	Definition
Baseline	Baseline is defined as the last available time point prior to T_0 on Day 1. Except for QSU, CO and COHb where the assessment prior to T_0 for each period will be used as a baseline.
T_0	The time of the product use on Day 1 and Day 3, corresponding to the first puffing of CHTP 1.1 M or mCC.

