11.6.2.3.2 Modified Cigarette Evaluation Questionnaire

The MCEQ domain scores composed of the three multi-item subscales and two single items from the MCEQ will be listed and summarized overall and by the two stratification factors (sex, mCC nicotine level at Admission) for the PK populations, as specified in Section 11.1.1 “Stratified Presentation”. The individual responses to all questions will be listed.

A mixed effects ANOVA model will be used to estimate mean CHTP 1.1 M - mCC differences of the MCEQ domain scores and variances, with a REML method (Bethesda,

2013; Brown and Prescott, 1999). Subjects within sequence will be used as random effects and fixed effects are period, sequence, and product exposure.

```
Proc mixed data=_data_ method=reml maxiter=200;
Class subject sequence product period;
Model response = sequence period product;
Random subject(sequence);
Lsmean product / pdiff =control('mCC') alpha=0.05 cl;
Run;
```

LS means for each product and the overall point and 95% interval estimate of the difference will be presented in the tables.

The data will be presented in the below outputs:

TFL number	Title
TABLES	
15.2.4.15	Analysis of MCEQ Subscales – PK Population
15.2.4.16	Descriptive Statistics of MCEQ Subscales – PK Population
15.2.4.16.1	Descriptive Statistics of MCEQ Subscales by Sex – PK Population
15.2.4.16.2	Descriptive Statistics of MCEQ Subscales by Nicotine Level – PK Population
LISTINGS	
15.3.6.12	Listing of MCEQ Questionnaire Results

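### Should the CO and COHb product comparison be adjusted for the pre-use baseline measured in each period?

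*SAP*

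**What the plan says.** SAP section 11.1.4 (Table 14) takes the last value before T0 on Day 1 as the general baseline and then makes an exception: "Except for QSU, CO and COHb where the assessment prior to" T0 in each period serves as that period's baseline. Section 11.6.2.2.1 collects these values. For COHb, "The first sample will be taken within 15 minutes prior to using the first product"; for exhaled CO, "On Day 1 and Day 3, the first test per day will be performed within 15 minutes prior to" T0.

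The same section then specifies a mixed model for exhaled CO and for log COHb. Its fixed effects are sequence, period, product, time point and product by time point, with a random subject effect and an unstructured covariance over time points. On the pre-use value it says: "The model will be evaluated including all of the different assessment timepoints, excluding the assessment prior to" T0. No baseline covariate appears in the model statement. Section 9 adds that "The main comparison between products will be the comparison over all time points".

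Section 11.6.2.3.1 (QSU-brief) takes over the CO model and adds the baseline score to it. The objective served by CO and COHb, in section 5.2, is "To describe the levels of carbon monoxide (CO) exposure for the CHTP 1.1 M as compared to mCC".

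**The concern.** A baseline that is defined specially for an endpoint and measured in both periods, but then left out of the main comparison, looks like an oversight. QSU-brief shares the Table 14 exception and does get the adjustment, which strengthens the impression.

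The random subject effect removes a subject's stable level, and the period effect removes the average Day 1 to Day 3 shift. What stays in the error is the subject's own difference in starting level between the two days. If that difference predicts the difference in post-use level, adjustment would narrow the confidence interval. Only the interval's width is at stake: sequence is randomised, so the unadjusted contrast is not biased by chance differences in starting level.

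**Working it through.** **Inputs.** The SAP gives no variance, correlation or precision figure for CO or COHb, so there is no planned figure to reproduce. The ±30% target in section 5.4.2 covers only the primary nicotine parameters. Section 8 gives 48 subjects and 5% drop-out: 48 × 0.95 = 45.6, taken as n = 46. Rho, as defined by the correlation of the two within-subject differences (pre-use and mean post-use), is an assumption, shown over a range.

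**1. Bias.** In a simulated 2×2 crossover (46 subjects, 4,000 runs, no product effect, no carry-over), the unadjusted estimate averaged within 0.002 of zero at every rho from 0 to 0.8.

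**2. Precision at matched degrees of freedom.** Adjusting the overall contrast for the within-subject baseline difference changes the 95% CI width by

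ratio = √[(1 − rho²)(1 + 1/(n − 4))] × t(n − 3) / t(n − 2).

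For n = 46 the factor without rho is √(1 + 1/42) × 2.0167/2.0154 = 1.0125.

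| rho | 0 | 0.2 | 0.3 | 0.5 | 0.7 |
|---|---|---|---|---|---|
| width ratio | 1.012 | 0.992 | 0.966 | 0.877 | 0.723 |

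Break-even is √(1 − 1/1.0125²) = 0.157. With 40 subjects the ratio at rho 0 is 1.015 and break-even is 0.170.

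**3. Precision against the SAP's code as written.** That code sets no degrees-of-freedom option. PROC MIXED with a RANDOM statement then uses the containment method, which here gives residual degrees of freedom:

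- COHb: 46 × 2 × 4 = 368 observations, less rank 46 + 1 + 1 + 3 + 3 = 54, leaves 314.
- CO: 46 × 2 × 3 = 276 observations, less rank 46 + 1 + 1 + 2 + 2 = 52, leaves 224.

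An adjusted analysis of subject-period means would have 43. The factor becomes 1.0118 × 2.0167/1.9675 = 1.037 for COHb and 1.0118 × 2.0167/1.9706 = 1.035 for CO. Break-even rises to 0.265 and 0.260. One may think the default too generous, but it determines the interval that would be reported.

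**4. What rho might be.** Suppose the baseline's correlation with the post-use value fades over the day. Rho for the mean over k times is the average correlation divided by √[(1 + (k − 1)r)/k], where r is the between-time correlation.

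- COHb, 0.5, 0.3, 0.1, 0 with r = 0.6: 0.225/√0.70 = 0.269.
- COHb, same with r = 0.8: 0.225/√0.85 = 0.244.
- CO, 0.5, 0.25, 0 with r = 0.6: 0.25/√0.733 = 0.292.

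The width ratios are 0.975, 0.982 and 0.968 at matched degrees of freedom, and 0.999, 1.006 and 0.990 against the code as written. In these assumed settings the gain is between 3% and nothing.

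Several features of the SAP could limit the baseline signal. Each period has "approximately 48 to 57 hours smoking abstinence and 1 day of single product use". Pre-use CO above 10 ppm counts as non-compliance and may lead to exclusion (section 11.4). Values below the quantification limit are generally set to half that limit (section 11.1.5), so any such baselines would be tied.

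**5. The obvious ways to adjust.**

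- *A change score* multiplies the width by √[2(1 − rho)]: 1.41 at rho 0, 1.18 at 0.3, 1.00 at 0.5.
- *Period baseline plus subject-mean baseline, one slope each, in the planned repeated-measures model.* In simulation (46 subjects, unit within- and between-subject SDs, 130 to 150 runs per setting), the fading COHb pattern gave an overall width ratio of 1.03 (r = 0.6) or 1.22 (r = 0.8), and 1.13 or 1.35 at 12 hours. The CO pattern gave 1.02 overall and 1.14 at the last time. Only a constant correlation (0.42 at all four COHb times, so rho 0.42/√0.70 = 0.50) gave a clear gain, 0.88 overall.
- *The same two terms fitted to each subject's post-use mean per period*, using the structure of the MCEQ model in section 11.6.2.3.2 ("Model response = sequence period product"). This avoids the widening, with 0.98, 0.98 and 0.96 in the three fading settings at matched degrees of freedom. But the overall contrast then comes from a different model than the time-point contrasts, and the likelihood handling of missing times is lost. The subject-mean baseline is also undefined for subjects with only one single-use day, whom section 10.3 admits.

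**The case for a change.** The strongest argument for adjustment is the asymmetry of the payoff. At matched degrees of freedom the loss is about 1% if the baseline carries no information, and the gain is about 12% at rho 0.5 and 28% at 0.7, with no new data needed. The SAP already adjusts QSU-brief within the same model family and gives no reason for treating CO and COHb differently.

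Part of this stands. The omission is real, adjustment would have been legitimate, and the gain would be material if rho were 0.5 or more. But nothing in the SAP supports a value that high, and the loss is nearer 4% than 1% against the intervals as coded.

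Adjustment also adds an assumption. The Day 3 baseline is measured after randomised Day 1 use. If it is shifted by λ in one sequence relative to the other, the adjusted contrast moves by slope × λ/2, and the data of a 2×2 design cannot easily show whether that move corrects or distorts.

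The QSU-brief contrast cuts the other way too. Authors who added baseline to one endpoint, and stated its exclusion from the response for the others, had the option in view. Nor is the Table 14 baseline idle for CO and COHb: section 11.6.2.2.1 summarises all scheduled time points on the single-use days, including the pre-use one.

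**Conclusion.** The concern does not hold. The planned CO and COHb comparison is a valid randomised within-subject contrast that directly answers a descriptive objective about levels. No hypothesis test and no precision target depends on it. Leaving out the baseline is a stated choice between two sound models.

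Its effect on precision cannot be determined from the SAP. With 46 subjects it lies between a loss of about 1% to 4% in interval width at rho 0 and a gain of about 10% to 12% at rho 0.5; the two ends of each range reflect the degrees of freedom assumed for the planned model. In the fading-correlation settings the difference is 3% or less either way. These figures rest on assumed correlations, complete data and no differential carry-over. A sponsor's statistician could reasonably choose either model, and nothing in the SAP has to be corrected.

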8 SAMPLE SIZE JUSTIFICATION

A total of 48 subjects will be randomized.

The estimates for the within-subject CV for nicotine C_{max} (60%) and $AUC_{(0-last)}$ (50%) are based on the data collected in the ZRHM-PK-05 clinical study (Bethesda, 2013) comparing the nicotine PK profiles of THS 2.2 M, another MRTP candidate, and mCC in a Japanese population.

The sample sizes of this study assume a 5% drop-out rate.

Sample size calculations were conducted using SAS[®] version 9.2 for the 95% CI of the mean differences between paired observations (proc power onesamplemeans) in the natural log scale (Senn, 2002). The SAS[®] implementation of the method published by (Beal, 1989) was adopted to estimate the probability of obtaining at most the target 95% CI of $\pm 30\%$.

A total of 48 subjects are needed to estimate the mean C_{max} parameter ratio between CHTP 1.1 M and mCC with a 80% probability of obtaining a margin of error (95% CI) of at most $\pm 30\%$, assuming that CHTP 1.1 M has a nicotine C_{max} similar to mCC (ratio equal to 1.00). This sample size is sufficient to provide 80% probability of obtaining a margin of error of at most $\pm 30\%$ for the $AUC_{(0-last)}$ ratio between CHTP 1.1 M and mCC, assuming a similar extent of nicotine absorption for the 2 products (ratio equal to 1.00).

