11.6.2.3 Questionnaires

11.6.2.3.1 Urge-to-Smoke Questionnaire of Smoking Urges Brief

The total score and the two factors from the QSU-brief will be listed for all scheduled time points and summarized overall and by the two stratification factors (sex, mCC nicotine level at Admission) for the PK population, as specified in Section 11.1.1 “Stratified Presentation”. This will also be done for the changes from baseline, the percent change from baseline and the maximum percent decrease over time. The percent change and the time to maximum percent decrease in total score will be summarized by product and analyzed using the Hodges-Lehmann method. The individual responses to all questions will be listed by product, study day, and assessment time points.

In addition line graphs will be produced for the total score and factors means (and 95% CI) over all timepoints.

The analysis of the subjective effects of smoking (the total score, and Factor-1 and Factor-2 from the QSU-brief) will be performed using the same mixed effects ANOVA

adopted for the analysis of CO breath test described in Section 11.6.2.2.1 “Exhaled CO and COHb”, including also the baseline score.

The main comparison will be the mean difference over all timepoints. LS means for each product, the overall mean difference and the mean differences at each time point will be presented in the tables as a point and interval (95% CI) estimate. Figures of the LS mean difference and 95% CI at each time point will be produced.

The data will be presented in the below outputs:

TFL number	Title
TABLES	
15.2.4.11	Analysis of QSU-brief Questionnaire Factors and Total Score – PK Population
15.2.4.12	Analysis of the Time to Maximum Percent Decrease in Total Score – PK Population
15.2.4.13	Descriptive Statistics of QSU-brief Questionnaire Factors and Total Score – PK Population
15.2.4.13.1	Descriptive Statistics of QSU-brief Questionnaire Factors and Total Score by Sex – PK Population
15.2.4.13.2	Descriptive Statistics of QSU-brief Questionnaire Factors and Total Score by Nicotine Level – PK Population
15.2.4.14	Descriptive Statistics of Time to Maximum Decrease in Total Score – PK Population
15.2.4.14.1	Descriptive Statistics of Time to Maximum Decrease in Total Score by Sex – PK Population
15.2.4.14.2	Descriptive Statistics of Time to Maximum Decrease in Total Score by Nicotine Level – PK Population
FIGURES	
15.1.2.9.1	QSU-brief Factors and Total Score Profiles Arithmetic Mean and 95% CI PK Population

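### Last covariance fallback (type=vc) for exhaled CO, COHb and QSU-brief drops within-period correlation, so the CI for the main product comparison can be too narrow; no df method is named

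*SAP*

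**What the plan says.** Section 11.6.2.2.1 of the SAP analyses exhaled CO and log COHb with PROC MIXED. The only random effect is subject within sequence ("Random subject(sequence"), and the covariance within a period is carried by the REPEATED statement: "Repeated time_point / subject=subject*product type=un". The MODEL statement has no DDFM option.

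The convergence rule reads "In case of model convergence issues, this will be reported in the study report and additional covariance structures will be investigated with the following order", followed by "heterogeneous compound symmetry (type=csh), heterogeneous autoregressive (type=arh) and variance component (type=vc".

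QSU-brief inherits this model through section 11.6.2.3.1, "including also the baseline score". Section 11.1.4 defines that baseline for QSU, CO and COHb as the pre-T0 assessment, which "for each period will be used as a baseline". Section 9 fixes the headline contrast for all three endpoints: "The main comparison between products will be the comparison over all time points".

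**The concern.** The product contrast compares one period with the other within a subject. Its error therefore depends on how strongly readings from the same product use move together beyond what the subject effect explains. Under un, csh and arh, the REPEATED block models that covariance. Under type=vc the block becomes diagonal, and the only correlation left is the constant one from the subject effect, which is the same within and across periods and cancels out of the contrast. Averaging several readings from one product use then looks more informative than it is.

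Contrasts at single time points suffer much less. The contrast over all time points, which the SAP calls the main one, suffers most.

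A second, smaller matter applies under every structure. With a RANDOM statement and no DDFM option, PROC MIXED uses containment. No random effect contains product, so its contrast gets residual degrees of freedom, although it rests on subject-level information.

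**Working it through.** **Inputs.** Section 8 randomizes 48 subjects and states "The sample sizes of this study assume a 5% drop-out rate": 48 × 0.95 = 45.6, taken as n = 46. Post-T0 readings per period, m: exhaled CO 3 and COHb 4 (section 11.6.2.2.1), QSU-brief 9 (section 7.3.2). The SAP gives no within-period correlation beyond the subject effect. It is called r here and assumed over a range.

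**The SAP's own figure.** The disputed rule states no number; the only SAP figure used is the sample size. For a 60% CV the SD of the log difference is √(2 ln(1 + 0.6²)) = 0.784. A 95% half-width of at most ln 1.3 with 80% probability needs 44 subjects; 44/0.95 gives 47, or 48 as an even total. AUC(0-last) at 50% CV needs 33. The 48 is reproduced and is not in question.

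**Degrees of freedom.** Default df = 2nm − [n + 2 + 2(m − 1)]:
- CO: 276 − 52 = 224
- COHb: 368 − 54 = 314
- QSU-brief: 828 − 64 = 764 (763 with the baseline covariate)

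Subject-level df = 46 − 2 = 44. The t multipliers are 1.971, 1.968 and 1.963 against 2.015. This alone makes the interval 2.2%, 2.4% and 2.6% too narrow, with coverage of about 94.4–94.5%.

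**Standard error under type=vc.** Set the within-subject variance to 1 and let readings within a period share correlation r. Then:
- variance that governs the product contrast: S = 1 + (m − 1)r, on 44 df
- variance on the remaining df: 1 − r
- residual variance that vc estimates: V = [44·S + (df − 44)(1 − r)] / df
- model SE / true SE = √(V/S)
- coverage ≈ 2Φ(t × √(V/S)) − 1

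With r = 0.3:

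| Endpoint | S | V | SE ratio | Coverage |
|---|---|---|---|---|
| CO | 1.6 | (44×1.6 + 180×0.7)/224 = 0.877 | 0.74 | 86% |
| COHb | 1.9 | (44×1.9 + 270×0.7)/314 = 0.868 | 0.68 | 82% |
| QSU-brief, no baseline term | 3.4 | (44×3.4 + 720×0.7)/764 = 0.855 | 0.50 | 68% |

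Coverage of the nominal 95% interval over the range of r:

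| Endpoint | r = 0 | 0.1 | 0.3 | 0.5 |
|---|---|---|---|---|
| CO | 95% | 92% | 86% | 79% |
| COHb | 95% | 91% | 82% | 73% |
| QSU-brief, no baseline term | 95% | 85% | 68% | 56% |
| QSU-brief, per-period baseline (simulated) | 93% | 84% | 72% | 64% |

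Simulated 2×2 crossovers agree with the first three rows to within about 1.5 percentage points. The last row comes from a REML random-intercept fit and assumes a between-subject SD equal to the residual SD.

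If correlation instead decays as AR(1), with adjacent r of 0.3 / 0.5, simulated coverage is 88/81% for CO, 86/79% for COHb and 85/76% for QSU-brief with baseline.

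For single time points, coverage stays at 91–95% for r up to 0.5.

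**With the correlation kept.** Using the subject-by-product error on about 44 df, simulated coverage is 94–95% in every setting.

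**The case against.** The strongest objection is that the step is remote. Un, csh and arh must all fail first, and all three model the within-period covariance. In 1,440 simulated complete, balanced, normal data sets, csh and arh each converged every time. The coverage figures describe vc as such and are not conditioned on three earlier failures. This stands as a limit on likelihood, although the fits were not made in SAS and real CO data may behave worse. Failure of the planned structure itself is most plausible for QSU-brief: a 9×9 unstructured matrix has 45 parameters, plus the subject variance, estimated from about 92 subject-period blocks for each of three scores.

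Next, the consequence is bounded. Convergence problems must be reported, the time-point contrasts are much less affected, these are secondary objectives to describe, section 11.1.7 rests no claim on individual intervals, and Cmax and AUC(0-last) use a separate model. All of this is true and sets the severity. But reporting a change of structure does not tell a reader that the interval is too narrow, and the QSU-brief analysis is among the topline outputs in section 12.3.

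The size also depends wholly on an assumed r, and at r = 0 the fault does no harm. That stands, and it is why a range is shown. The lowest QSU-brief figures need a constant r = 0.5 from 15 minutes to 12 hours. The 93% for QSU-brief with baseline at r = 0 cannot come from within-period correlation; it belongs to the baseline term under the simulated settings and should not be counted towards this point.

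Finally, the supplied code determines the df through the software default, so the result is reproducible and the effect is small. Both are correct. The default still does not match the information behind the contrast, and naming a method costs nothing.

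**Conclusion.** The point holds as a minor correction. The planned unstructured model is sound for the overall product contrast apart from the small df effect. The prespecified last fallback is not: it understates the error of the stated main comparison whenever readings after the same product use are positively correlated beyond the subject effect. At r = 0.3 the vc interval has about 0.74 × 0.978 = 0.73 of the valid width for CO and 0.68 × 0.976 = 0.66 for COHb.

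These figures assume 46 complete subjects, equal correlation within a period and an r that the SAP does not supply; decaying correlation gives a smaller loss. The df effect, intervals 2.2–2.6% too narrow, applies on the planned path as well. The sample size and the primary analysis are unaffected.

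**What to change.** In the fallback list of section 11.6.2.2.1, replace type=vc with type=cs. Alternatively, keep vc and, at that step only, add a random subject*product effect. Do not add that effect alongside cs or csh, where it is confounded, or nearly so, with the REPEATED block. Add ddfm=kr to the MODEL statement for CO and COHb, and state in section 11.6.2.3.1 that it also applies to QSU-brief.

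The cost is one word in the list and a few words of SAS code. Intervals become slightly wider under the planned structure because of the df. No further data are needed. If the SAP can no longer be amended, section 3 already provides for describing the change in the study report.
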